5.1.5 Participant Payment. Participants are eligible to be remunerated up to \$380 if enrolled (if excluded after the in-person screening, \$50 for attending the screening). The disbursements will be distributed such that for enrolled participants, \$100 will be paid after completion of Baseline Visit 2, up to \$180 after Exercise Visit 36 (prorated at a rate of \$5/session if participants do not attend all 36 sessions), and \$100 after completion of follow-up visit two. The payments will be in the form of a check mailed to the participant's home.

5.1.6. Risks and Minimization of Risks.

Exercise: The completion of maximal exercise always involves risks of death, acute myocardial infarction, and complications that require hospitalization. Importantly, exhaustion, fatigue, and muscle soreness are associated with maximal exercise, but are temporary symptoms. Additionally, there is a risk of falling when performing walking exercise on a treadmill and when performing the timed 25-foot walk (T25FW) and six-minute walk (6MW) tests. Other risks of completing treadmill walking exercise, the T25FW test, and the 6MW test include arrhythmia, musculoskeletal injury, and difficulty breathing. Some MS patients are thermosensitive with symptoms temporarily increasing or worsening with a large rise in core body temperature. We note that MS patients are able to complete a maximal exercise in a room temperature laboratory without any adverse symptoms arising [29,30]. Risks associated with the stretching and toning activities include strains, cramps, and musculoskeletal injury; however, these risks are small as the stretching and toning activities are performed at minimal exercise intensity, and derive from the NMSS guidelines for stretching with MS.

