The risks of exercise will be minimized by screening for individuals with factors placing them at increased risk for complications. This includes an initial health risk screening to minimize the risk of cardiovascular complications during maximal and submaximal exercise [31,32]. This procedure further is consistent with American Heart Association recommendations for exercise testing [33]. Importantly, although increasing age is a risk factor for cardiovascular disease, there is no evidence that age *per se* is a strong predictor of exercise-associated cardiovascular complications, and the referral of individuals for medical clearance solely based on age is associated with unnecessary health care referrals [32]. Additionally, participants with MS will be ambulatory without assistance, relapse free for 30 days, and will not have acutely taken steroids in that time period. These criteria will allow for healthy samples of MS patients. Further, all personnel are trained in CPR and emergency lab procedures. To minimize the risks of exhaustion, fatigue, and muscle soreness associated with aerobic exercise, participants will be encouraged to warm-up and/or stretch before any assessment of exercise. To minimize the risk of falling when walking on the treadmill, we will encourage the use of handrails on the treadmill as well as having a gait belt around the participant's waist and two research assistants within

arm's reach. To minimize the risk of overheating, given that some persons with MS are thermosensitive, the testing environment will be controlled with an air conditioner (i.e., manipulated by keeping the ambient air temperature below normal room temperature) and there will be fans that blow air directly on the participant. Participants will further wear clothing appropriate for exercise. Such environmental regulation will keep the participant cool during the sessions and avoid symptom exacerbation.

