Functional Outcomes: There exists some minor but unlikely psychosocial risk associated with the completion of psychological questionnaires. For example, some participants might experience embarrassment or anxiety in responding to some questions. The assessment of ability to perform activities of daily living and functional mobility (i.e., Life-Space Mobility Assessment) involve activities that are common in everyday life. Thus, a risk for a fall during these activities is no greater than what these individuals would experience in a normal day.

In the context of functional testing, a research assistant will be standing next to the participant to provide the subject with support if they were to lose their balance. This will provide an added measure of safety that is not present in their normal activities. In the event that a participant has difficulty comprehending any assessment, we will verbally summarize the objective in lay language, and if necessary, will read the questionnaire instructions out loud. To minimize the risks associated with the T25FW test, we will have multiple research assistants within arm's reach at all times, per standardized protocol [34]. In the event that a participant has

difficulty comprehending any assessment, we will verbally summarize the objective in lay language, and if necessary, will read the questionnaire instructions out loud.

5.1.7 Special Populations. Pregnant women, human fetuses and neonates will not be included in the study. Additionally, children and prisoners will not be included in the study. Adverse events will be immediately reported to the study Statistician and Safety Officer, in addition to the Kessler Foundation IRB.

5.1.8 Informed Consent. The PI, Project Coordinator, or Research Assistants will present the study at the in-person screening visit and ample time will be allotted for potential participants to ask questions and have them answered by study personnel. The consent form will be reviewed page by page, and again time will be allotted for questions and answers. Finally, when the study protocol and consent have been reviewed and all questions have been addressed, individuals agreeing to participate will sign the consent form. Each participant will be given a copy of her signed consent form (by email). All conversations regarding the study will be held in a private setting (i.e., a testing room within Kessler Foundation's Neuroscience and Neuropsychology Laboratory).

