3	7-9	50-60% VO ₂ R/HRR	20-25 min	Improvement
4	10-12	50-60% VO ₂ R/HRR	25-30 min	Improvement
5-6	13-18	60-70% VO ₂ R/HRR	25-30 min	Improvement
7-8	19-24	60-70% VO ₂ R/HRR	30-35 min	Improvement
9-10	25-30	70-80% VO ₂ R/HRR	30-35 min	Maintenance
11-12	31-36	70-80% VO ₂ R/HRR	35-40 min	Maintenance
Follow-up Testing				

exercise training itself will be led by trained exercise leaders (i.e., research assistants) who are not involved in the collection of outcome assessments at Kessler Foundation under the supervision of [name]. At the outset of each session, participants will be fitted with a Polar HR Monitor (Oy, Finland), and HR will be monitored continuously throughout each session. Each session will begin with a 5-10 min warm-up, followed by the exercise; the target heart rate reserve (HRR) range associated with the VO₂R range will be maintained for as long as possible during each exercise period. This will be followed by a 5-10 min cool-down. Importantly, under the supervision of [name], with guidance from [name] at the University of Alabama at Birmingham, we will apply highly developed principles and techniques associated with Social Cognitive Theory to maximize adherence and compliance with the intervention. This will involve certified exercise leaders delivering topics for enhancing adherence and compliance (i.e., self-efficacy, goal setting, overcoming barriers to exercise, monitoring of performance feedback, promotion of realistic outcome expectations, importance of social support) during actual exercise training sessions. Participants will complete an exercise log at the conclusion of each session for better characterizing the experience with the intervention. Log data will include perceived exertion [67], well-being, enjoyment, and mental/physical fatigue.

At the conclusion of exercise sessions 1, 7, 13, 19, 25, and 31, participants will be invited to engage in discussions with the exercise leaders regarding adherence and compliance that will last approximately 30 minutes following those sessions. These sessions will be led by the exercise leader under the supervision of [name], and with guidance from [name], will involve the delivery of information based on Social

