As is the case for the experimental condition, HR will be monitored throughout each session. To minimize attrition, as is the case for the intervention condition, under the supervision of [name], with guidance from [name], certified exercise leaders will apply highly developed principles and techniques associated with Social Cognitive Theory for enhancing participant adherence and compliance to the stretching-and-toning prescription during each session. Participants will complete a stretching-and-toning log at the conclusion of each session for better characterizing experience with the intervention. Log data will include perceived exertion [67], well-being, enjoyment, and mental/physical fatigue. All participants will further be asked to not undertake additional exercise (i.e., not join a gym and begin exercising) or engage in cognitive rehabilitation over the study period.

At the conclusion of stretching-and-toning sessions 1, 7, 13, 19, 25, and 31, participants will be invited to engage in discussions with the exercise leaders regarding adherence and compliance that will last approximately 30 minutes following those sessions. These sessions will be led by the exercise leader under the supervision of [name], and with guidance from [name], will involve the delivery of information based on Social Cognitive Theory principles for enhancing adherence and compliance [68]. Specifically, this involves the provision of newsletters and opportunities to ask questions on topics such as outcome expectations, facilitators and barriers to exercise, goal setting, social support, and self-efficacy. An example newsletter on outcome expectations is attached in this application.

Participants will be remunerated \$5 per treadmill walking exercise/stretching-and-toning visit attended (i.e., up to \$180). The final remunerated amount will be delivered to participants after attending the last visit in the form of a check.

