exploring and examining the impact of such losses, as we could have upwards of 25% drop-out, given that this sample includes persons with objective CPS impairment. Initially, analyses will be done on the data set using last observation carried forward and then on the actual data collected (case-wise deletion), followed by multiple imputation for missing data. All analyses at present are planned using SPSS software (version 25 or higher), although as new options continue to evolve with SAS or R; these will be considered if there are new tools for imputation that will help understand the impact of missing data. We believe that these imputations should involve fewer than 15% of the participants, which then should have minimal impact on the analyses. However, it is important to assess this from a best case and worst case scenario and if the results are consistent, then we can be more confident of our findings. If these analyses yield differing results – more exploratory analyses are required to understand if the differences in the outcomes are coming from the control condition or the intervention condition. If the control condition, the implications can be examined in one way and if the intervention condition, it is likely to add cautionary notes to the findings.

Interim and Final Analysis. We do not plan any interim efficacy or futility analyses. The study team will work together for publications on the protocol, fidelity monitoring plan, as well as the primary study outcomes.

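### Apart from fatigue, the session log lists none of the named exercise harms, and the plan states no record of reasons for stopping and no harms summary by arm

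*Combined protocol and SAP*

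**What the plan says.** Protocol section 5.2.5 (treadmill arm): "Participants will complete an exercise log at the conclusion of each session for better characterizing the experience with the intervention". Section 5.2.6 (control arm): "Participants will complete a stretching-and-toning log at the conclusion of each session". The content is described in the same words for both arms: "Log data will include perceived exertion [67], well-being, enjoyment, and mental/physical fatigue". The schedule is 36 sessions per participant in each arm (5.1.4).

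Section 5.1.6 sets out the exercise risks. For exertion it says: "Importantly, exhaustion, fatigue, and muscle soreness are associated with maximal exercise, but are temporary symptoms". It adds falls on the treadmill and temporary worsening of MS symptoms with heat, and then: "Other risks of completing treadmill walking exercise, the T25FW test, and the 6MW test include arrhythmia, musculoskeletal injury, and difficulty breathing". For the control activities it names strains, cramps and musculoskeletal injury.

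The route for adverse events is one sentence in section 5.1.7, Special Populations: "Adverse events will be immediately reported to the study Statistician and Safety Officer, in addition to the Kessler Foundation IRB".

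Under section 5.3 and the SAP's Statistical Analysis section, dropouts are handled by last observation carried forward. The SAP's Treatment of Missing Data section adds case-wise deletion and multiple imputation. If these disagree, "more exploratory analyses are required to understand if the differences in the outcomes are coming from the control condition or the intervention condition".

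**The concern.** The log is the one form that every participant completes at every attended session, and its listed items describe how the session felt rather than what went wrong. It is tied to attendance, so a participant who is hurt or worsens between sessions and does not return completes no further log. The reporting sentence in 5.1.7 says where an adverse event goes once known. It gives no definition, no question to ask and no schedule for asking.

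Two things are at stake. The SAP calls the trial Phase I/II, and section 5.3 says its effect sizes will inform a multi-site Phase II/III trial; how well the exercise was tolerated against control would be useful there too. Reasons for stopping also bear on the primary analysis, because a participant who leaves without follow-up testing has the baseline SDMT score carried forward. Analysts cannot fill in later what was never asked.

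**Working it through.** **1. Named harms against listed log items**

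| Harm named in 5.1.6 | Attached to | Listed log item (5.2.5, 5.2.6) |
|---|---|---|
| Fatigue | Maximal and aerobic exercise | Yes |
| Exhaustion | Maximal and aerobic exercise | Partly, through perceived exertion |
| Muscle soreness | Maximal and aerobic exercise | None |
| Falls | Treadmill walking | None |
| Musculoskeletal injury | Both arms | None |
| Breathing difficulty | Treadmill walking | None |
| Arrhythmia | Treadmill walking | None (heart rate is monitored at sessions in both arms) |
| Heat-related worsening | Exercise | None |
| Strains, cramps | Control activities | None |

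Death, myocardial infarction and complications needing hospital care are also named. A session log would not be expected to be the means of finding those.

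**2. Other places where harms or reasons could be picked up**

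- 5.1.7: reporting route only.
- 5.2.5 and 5.2.6: six discussions by invitation, about adherence and compliance, with no stated recording of harms.
- 5.2.7: the coordinator's contact after the last session is to schedule testing. Follow-up repeats the baseline procedures, but reaches only those who return.
- 5.3 and the SAP: no harm outcome, no harms table, no record of why a participant stopped.

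**3. The plan's own sample size, reproduced**

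Inputs: partial eta-squared 0.11, alpha 0.05, power 0.80 (5.1.1 and SAP Sample Size Considerations).

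- f² = 0.11 / (1 − 0.11) = 0.1236, so f = 0.352.
- ANCOVA with two groups and one covariate, noncentrality f² × N: the smallest N with power of at least 0.80 is 66 (power 0.803).
- 66 / 0.75 = 88.

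The plan's figures stand and the point does not touch them.

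**4. Scale**

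- Scheduled sessions: 44 × 36 = 1,584 per arm; 2 × 1,584 = 3,168 in all.
- Attrition allowance: 0.25 × 88 = 22. The SAP expects imputation for fewer than 15% of participants: 0.15 × 88 = 13.2.
- If 22 people stopped at times spread evenly over the schedule (an assumption), they would miss on average 18 sessions each: 22 × 18 = 396 logs, and 396 / 3,168 = 12.5%.

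**5. Link to the primary analysis**

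The SDMT is an outcome at baseline and follow-up only. For a dropout without follow-up testing, the imputed follow-up score equals the baseline score and the change is 0. A participant who left because of worsening and one who left for an unrelated reason get the same value.

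**6. What full capture could show with 44 per arm**

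The documents give no harm rates, so those below are assumptions.

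- No events in an arm: one-sided 95% upper bound 1 − 0.05^(1/44) = 6.6%.
- Chance of at least one event, 1 − (1 − p)^44: 59%, 90% and 99% for p = 2%, 5% and 10%.
- Power for a difference, Φ[(|p₁ − p₂| − 1.96·s₀)/s₁], where s₀ is the pooled and s₁ the unpooled standard error. For 10% v 30%: s₀ = √(2 × 0.2 × 0.8/44) = 0.0853 and s₁ = √((0.09 + 0.21)/44) = 0.0826, so power = Φ(0.40) = 0.66. For 5% v 15%: 0.34.
- If only half of events are captured in each arm, a true 10% v 30% appears as 5% v 15%, and power falls from 0.66 to 0.34.

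**The case against.** A reader might infer more than the documents support, in five ways.

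- *The log asks about none of the named harms.* Not so: fatigue is a named risk and a log item in both arms, and exertion and well-being are partly relevant.
- *Harms cannot be compared at all.* Too strong. Reports under 5.1.7 are not restricted by arm and could be tabulated by arm, and logged fatigue can be compared. What is lacking is any stated solicitation and any planned summary.
- *Treadmill participants are watched more closely, so detection is unequal.* Section 5.1.6 does provide for "having a gait belt around the participant's waist and two research assistants within" arm's reach, but nearby sentences there concern exercise assessments and the testing environment. The training description in 5.2.5 mentions no such pair. Sections 5.2.5 and 5.2.6 otherwise match: trained leaders, heart rate monitoring, the same log content, the same six discussions. Unequal observation is suggested, not established.
- *The SAP's tracing of missing-data differences to an arm needs reasons for stopping.* It does not; the assigned arm is known for everyone randomised. Reasons are needed only to interpret a difference once it has been located.
- *Twenty-two people will leave with no reason recorded.* That is a conservative allowance combined with an assumed absence of recording. The list of log items may not be exhaustive, the form is not in the text, and the operating manuals and fidelity plan that the SAP mentions are not visible.

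It is also fair to say that safety is not a stated aim or outcome, that the SDMT sample size is unaffected, and that power for harms would be low even with full capture. These points limit the weight of the concern. They do not supply harm questions, contact after stopping, reasons for stopping or a table.

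**Conclusion.** The point holds as a cheap improvement, not as a flaw in the primary analysis. Apart from fatigue, the listed log items do not cover the exercise harms that the protocol names, and the log ends when attendance ends. The documents state no solicitation of adverse events, no record of why participants stop and no summary of harms by arm. On that text, harms cannot be reliably compared between arms, and harm-related dropout cannot be separated from other dropout.

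The size cannot be put as a bias. The 3,168 sessions and 22 dropouts are planned maxima. The illustrative loss of power from 0.66 to 0.34 rests on assumed harm rates and an assumed capture of one half. The conclusion assumes that the log form and manuals add nothing beyond what the protocol and SAP describe; if they already hold such items, what remains is to state them and add the table.

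**What to change.** - **Logs.** Add identical yes/no items to both arms' existing logs: since the last session, any fall; any injury or activity-limiting pain; any new or worse MS symptom; any medical contact; each with its date.
- **Missed sessions and stopping.** Have the existing coordinator ask the same items, and the reason, when a participant misses sessions or stops. Ask the items again at Follow-Up Visit 1.
- **Routing.** Send positive answers through the reporting route already in 5.1.7.
- **SAP.** Add one descriptive table by randomised arm: participants with each event, events per session attended, and reasons for stopping. Read any disagreement between the missing-data analyses alongside the reasons.

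The cost is about a minute per session, short calls, one table and a higher count of minor events. Sample size, exercise prescription and primary analysis do not change. Most enrolment is still planned at the current site (65 in section 5.1.1, 72 in the SAP), so an early change would cover most participants. For those already treated, the table should say that the items were not asked.

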The primary analysis will involve a statistically efficient, hierarchical step-down testing approach using ANCOVA models to examine differences in post-test outcomes of CPS and thalamocortical RSFC (i.e., examining group differences in follow-up outcomes, adjusting for baseline as covariate). The hierarchical step-down approach presents a series of conditional hypothesis tests after the primary hypothesis is assessed. This *a priori* specifies the importance and order of the testing so that each hypothesis is tested in order, until the first non-significant result occurs. Once a null-hypothesis is not rejected, all formal testing will stop, and all subsequent results will be reported as *post-hoc* and/or descriptive. This protects against Type I error as it assumes that the outcomes are correlated, and the overall *p*-value is protected by reporting the largest *p*-value for all the tests. As the primary study outcome involves CPS based on SDMT scores, we will first perform an ANCOVA model on follow-up SDMT score, with group (intervention or control) as a between-subjects factor and baseline SDMT score as the covariate. If statistically significant (i.e., *p*<.05), we will then assess the effects of the intervention on the general construct of CPS using MANCOVA and on the individual CPS tests using separate, univariate ANCOVA models.

Regarding thalamocortical RSFC, the next set of analyses will involve performing ANCOVA models on follow-up RSFC between the thalamus and frontal cortical areas (e.g., SFG, MFG [21]), respectively, with group (intervention or control) as a between-subjects factor and baseline RSFC between the thalamus and frontal cortical areas, as the covariates. We will require an alpha of .05 (corrected for multiple comparisons) for significance for thalamocortical RSFC outcomes. The correction for multiple comparisons will be achieved by establishing a suitable voxel cluster-level threshold through Monte Carlo simulations (using the 3dClustSim program, part of the AFNI suite of image analysis programs). Based on our pilot work [19,21], we expect significant group differences in SDMT score and RSFC between the thalamus and frontal cortical areas, respectively, at follow-up after controlling for baseline scores, whereby participants who are randomly assigned to the intervention group will demonstrate greater SDMT scores and stronger thalamocortical RSFC at follow-up compared with those who are randomly assigned to the control group.

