Specific Aim 1. The primary analysis will involve a statistically efficient step-down testing approach using ANCOVA models to examine changes in CPS and thalamocortical RSFC (i.e., examining group differences in follow-up outcomes, adjusting for baseline). As the primary study outcome involves CPS based on SDMT scores, we will first perform an ANCOVA model on follow-up SDMT score, with group (exercise or control) as a between-subjects factor and baseline SDMT score as the covariate. If statistically significant (i.e., $p<.05$), we will then assess the effects of the intervention on thalamocortical RSFC. This second step will involve performing two separate ANCOVA models on follow-up RSFC between the thalamus and right MFG and ACC, respectively, with group (exercise or control) as a between-subjects factor and baseline RSFC between the thalamus and right MFG and ACC, respectively, as the covariates. We will require an alpha of .05 (corrected for multiple comparisons) for significance for thalamocortical RSFC outcomes. The correction for multiple comparisons will be achieved by establishing a suitable voxel cluster-level threshold through Monte Carlo simulations (using the 3dClustSim program, part of the AFNI suite of image analysis programs). Based on our pilot work¹², we expect significant group differences in SDMT score and RSFC between the thalamus and right MFG and ACC, respectively, at follow-up after controlling for baseline scores, whereby participants who are randomly assigned to the exercise group will demonstrate greater SDMT scores and stronger thalamocortical RSFC at follow-up compared with those who are randomly assigned to the control group.

Specific Aim 2. We will examine RSFC between thalamus/right MFG, and RSFC between thalamus/ACC, respectively, as two potential mediators of the effects of TMWX training on CPS, consistent with the methodologies of Baron and Kenny⁸⁹ and MacKinnon et al⁹⁰. This statistical mediation approach is consistent with the proposed gold standard approach for examining exercise-related mechanisms of cognitive

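### After a significant SDMT, protocol section 5.3 and the SAP give different second steps, and section 5.3 does not say whether the other CPS tests gate RSFC, a primary outcome

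*Combined protocol and SAP*

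**What the plan says.** Protocol section 5.3 (Analysis) describes a "hierarchical step-down testing approach using ANCOVA models to examine differences in post-test outcomes of CPS and thalamocortical RSFC", so CPS and RSFC sit in one hierarchy. Its stop rule is "Once a null-hypothesis is not rejected, all formal testing will stop", with everything after that point reported as post-hoc or descriptive. SDMT comes first. If it is significant, "we will then assess the effects of the intervention on the general construct of CPS using MANCOVA and on the individual CPS tests" follows. A new paragraph then begins "Regarding thalamocortical RSFC, the next set of analyses will involve performing ANCOVA models on follow-up RSFC between the thalamus and frontal cortical areas".

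The SAP (Specific Aim 1) uses the same first test at the same level. If it is significant, "we will then assess the effects of the intervention on thalamocortical RSFC", and the SAP calls this the second step. No CPS MANCOVA stands between the two.

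The regions also differ. Section 5.3 gives them by example only: "RSFC between the thalamus and frontal cortical areas (e.g., SFG, MFG [21". The SAP names right MFG and ACC without qualification, in Specific Aim 1 and again as the two mediators in Specific Aim 2.

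The Abstract and the SAP's opening section (Statistical Design and Power) both list RSFC as a primary outcome beside SDMT. Section 5.2.1 labels the CPS measures other than SDMT exploratory. Nothing in the documents says which text governs.

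**The concern.** In a fixed-sequence procedure the order decides which results may be claimed formally. Here two current texts place a primary outcome at different positions. In section 5.3, tests labelled exploratory elsewhere in the same protocol come between SDMT and RSFC, and the stop rule exempts none of them. Section 5.3 also does not say what a CPS gate would be: the MANCOVA, every individual test, or neither.

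What is at stake is the reporting status of RSFC, formal or descriptive, in trials where SDMT succeeds and the other CPS measures do not follow. A team that has not settled the order beforehand could settle it after seeing which version suits the data.

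**Working it through.** **1. The plan's own figure.** Inputs from the SAP (Sample Size Considerations): partial eta-squared 0.11, alpha 0.05, ANCOVA F test with one baseline covariate, N = 66. Then f² = 0.11/0.89 = 0.1236, f = 0.3516, and the standardised difference is 2f = 0.70 SD. With noncentrality f² × N and 1 and 63 degrees of freedom, power is 0.803 (N = 65 gives 0.797). So 66 reproduces, and 66/0.75 = 88. SDMT power is therefore about 0.80.

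**2. The orders side by side.** Formal status of RSFC:

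| SDMT | CPS gate | SAP | Section 5.3, CPS tests as gate | Section 5.3, CPS tests alongside |
|---|---|---|---|---|
| not significant | any | not formal | not formal | not formal |
| significant | passes | formal | formal | formal |
| significant | fails | formal | post-hoc or descriptive | formal |

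The texts part only in the last row, and only if the CPS tests are a gate.

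**3. How often the last row occurs.** The quantity is P(SDMT significant and CPS MANCOVA not significant). The documents give no CPS effects, no correlations and no MANCOVA power, so these are assumptions.

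- Simple arithmetic, test statistics independent: 0.803 × (1 − MANCOVA power). Power 0.5 gives 0.803 × 0.5 = 0.40; power 0.8 gives 0.803 × 0.2 = 0.16. With a correlation of 0.9 between the two statistics and power 0.8, simulation gives 0.05.
- Fuller simulation: 33 per arm, SDMT effect 0.70 SD, the five other CPS tests in section 5.2.1, baseline to follow-up correlation 0.7, Wilks' lambda with all baselines as covariates, 10,000 trials per cell. The three figures in each cell are for inter-test correlations of 0.3, 0.5 and 0.7.

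| Effect on the other CPS tests | SDMT outside the MANCOVA | SDMT inside the MANCOVA |
|---|---|---|
| 0.70 SD | 0.072, 0.152, 0.222 | 0.067, 0.166, 0.261 |
| 0.50 SD | 0.306, 0.412, 0.478 | 0.214, 0.330, 0.367 |
| 0.35 SD | 0.550, 0.598, 0.635 | 0.335, 0.369, 0.324 |

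The range is about 0.07 to 0.64. With 44 per arm, 11 of them carried forward from baseline, the three rows become 0.09–0.28, 0.23–0.48 and 0.33–0.62.

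**4. Type I error.** Take a real SDMT effect (power 0.803), no effect on the other CPS tests or RSFC, and one RSFC test at a joint .05.

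- RSFC false positives, SAP order, under independence: 0.803 × 0.05 = 4.0%.
- RSFC false positives, section 5.3 with a CPS MANCOVA gate: 0.803 × 0.05 × 0.05 = 0.2%.
- Order chosen after the data: every trial that claims RSFC with the extra gate also claims it without, so the RSFC rate cannot exceed the SAP-order rate.
- If a CPS MANCOVA success also counts as a confirmatory claim, the chance of at least one false claim is 0.803 × (1 − 0.95²) = 7.8% under independence, and 6.5–7.6% in simulation with correlated tests.

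**The case against.** The strongest reply is that section 5.3 never makes RSFC conditional on the CPS tests. Its significance condition stands only before the CPS MANCOVA and ANCOVAs. RSFC opens a new paragraph without one, and the closing expectation mentions only SDMT and RSFC. Section 5.2.1 calls the other CPS tests exploratory and gives their purpose as generalisability. The SAP treats cognitive outcomes beyond SDMT as exploratory. Read so, SDMT gates RSFC, the CPS tests run alongside, and the two texts agree on RSFC's status.

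This stands in part: a CPS gate is an inference, not a stated rule. But the alongside reading is not stated either. It has to be set against a scope sentence covering both CPS and RSFC, a stop rule without exemptions, and a sentence about "reporting the largest *p*-value for all the tests", which treats the tests as one chain. The text favours a gate without settling it.

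A reader might also infer that the conflict inflates the trial's Type I error. The documents do not support that as a general statement. The 6.5–7.6% counts false positives on a CPS MANCOVA that section 5.2.1's label would make exploratory; for RSFC alone there is no inflation beyond the SAP order.

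Nor can a reader infer that the SAP prevails. It differs from the protocol elsewhere (72 against 65 participants at the second site, and a different daily-living measure), and neither text is identified as the later one. Finally, the section 5.3 regions are examples and MFG appears in both texts, so the SAP might be narrowing an open list. SFG is nevertheless absent from the SAP, and ACC is not named in section 5.3.

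**Conclusion.** The concern holds as an unresolved order. After a significant SDMT the second steps differ, and section 5.3 leaves the role of the CPS tests unstated. On the reading its own wording favours, RSFC changes from formal to post-hoc or descriptive when a CPS gate fails. On the softer reading the texts agree on RSFC's status. The mismatch in regions stands under either reading.

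The SDMT test and its conclusion are the same under both texts, and either order, fixed in advance, controls Type I error. The 0.07 to 0.64 probability of disagreement depends on assumed CPS effects and correlations; it shows that the case is not remote, and is no forecast. The 4% RSFC rate assumes SDMT power of 0.80 and a correction that holds RSFC at a joint .05. This should be fixed, but it does not threaten the SDMT result.

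**What to change.** Before any unblinded analysis, reconcile section 5.3 and the SAP's Specific Aim 1 to one pre-specified order. The order consistent with the documents' own labels is SDMT at .05, then RSFC only if SDMT is significant, with the CPS MANCOVA and individual CPS ANCOVAs declared exploratory and outside the formal chain. The reason is that RSFC is primary and the other CPS tests are exploratory, not that the SAP takes precedence.

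Use one closed region list in section 5.3, Specific Aim 1 and the Specific Aim 2 mediators. Right MFG and ACC are the only regions named without qualification, but the choice is scientific. Both texts correct RSFC by "establishing a suitable voxel cluster-level threshold through Monte Carlo simulations"; state whether that correction spans both regions. If it does not, test the regions in a fixed order or with Holm. A fixed order fits the largest-p-value sentence in section 5.3; Holm would need that sentence replaced by Holm-adjusted p-values.

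The cost is a few text edits and one decision on regions. The other CPS tests would carry no formal claim. The second region would be tested only conditionally under a fixed order, or some power would be lost under Holm. The documents do not allow that loss to be sized, because a plain ANCOVA calculation ignores the cluster-level threshold.
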